Recordings of telephone interviews will be captured on a digital recorder. Digital audio recorders will be kept in a locked drawer when not in use. Digital files of recorded telephone interviews will be transferred to the VAPORHCS server. Here they will be saved in a location only accessible to approved study team members.

Benefits

The participants in the hearing aid study may benefit if the low-gain amplification helps them to be less bothered by their tinnitus. Even though all individual participants may not personally benefit, the results of this study may lead to a future larger study, which could in turn provide evidence to support the expanded use of low-gain amplification for bothersome tinnitus. All participants in clinician interviews will be VA staff and clinicians. Although no direct benefit to the VA staff or clinicians is expected, responses will inform a future study that may lead to evidence to support the spread of this practice in VA clinics. In this case, more Veterans with normal hearing thresholds and bothersome tinnitus could benefit from the research.

Protected Health Information:

HIPAA identifiers will include names, geographical subdivisions smaller than a state, dates (date of birth—DOB—and study contact dates), telephone numbers, emails, and social security numbers (SSNs). This information is the minimum necessary to contact subjects, enroll them in the study, and carry out the study protocol. Phone numbers and address are needed to ensure that subjects may be reached for follow-up visits and other study-related communication. Full SSN and DOB are needed to verify records exist in CPRS for subjects or enroll any subjects in CPRS who do not already have a record there for the purpose of entering study-related notes.

Resources Available

Necessary equipment for this project is available at the National Center for Rehabilitative Auditory Research (NCRAR), VA Portland Health Care System (VAPORHCS), where the

Principal Investigator (PI), [name], and the core research team have offices and research space allocated for their usage in a variety of ongoing projects. A double-walled booth and adjacent control room are dedicated to the PI's projects.

Audiometric test equipment includes a GSI audiometer and middle ear analyzer. Multiple computers are available for use in the lab, including one that is networked with access to the VAPORHCS server and to the Internet. Several different kinds of earphones are available, including the ER3 earphones that came with the audiometer. Two Larson Davis sound level meter systems are available. The hearing aid laboratory has a Fonix 7000 Hearing Aid Test System, Starmed Otolab Professional Finishing System, and an AuraCare hearing aid cleaning and modification station. Other equipment in the lab may be used on an as-needed basis. For example, additional audio test and measurement equipment is available to verify the output of the hearing aids

Data storage, analysis, and preparation of manuscripts and presentations will be performed digitally using a combination of hardware and software systems already in place at the NCRAR. The VAPORHCS will maintain backups and data security for the project in compliance with the VA federally-mandated responsibility for oversight of all data collected as part of research conducted at a VA facility. No direct costs will be incurred by the use of this system. The procedures will be overseen and approved by the VAPORHCS Institutional Review Board.

Costs To Subjects

A Veteran participant will not be required to pay for care and services (treatment) received as a subject in a VA research project. Some Veterans are also required to pay co-payments for medical care and services provided by VA that are not part of this study (e.g., normal hospital and prescription expenses that are not part of the research study, any treatment that is standard clinical treatment). The study may include non-Veterans, who will incur no costs. The VA audiologists in Aim 2 will incur no costs.

Subject Compensation

The research participants in Aim 1 will receive \$20 for each appointment, an amount consistent with our other studies, which will cover typical travel costs associated with attending the appointments. The VA audiologists participating in clinician interviews will not receive compensation.

Privacy and Confidentiality

Subjects' information used for this study will be kept confidential as required by law. The results of their participation in this study may be used for publication or for scientific purposes, but the results will not include any information that could identify them. Their identity will not be disclosed unless they give specific, separate consent or if required by law. Current VA regulations require us to keep study records indefinitely.

At the end of their study participation, subjects from Aim 1 will be allowed to keep the hearing aids used during the study. In order to maintain the product warranty on the hearing aids once ownership passes to the subject, the subjects' name and device serial numbers must be disclosed to the hearing aid manufacturer, Widex, upon their completion of the study. This information will be provided by telephone or fax (fax transmissions will be scheduled on both ends to ensure that the fax transmission is immediately received by the intended party); it will not be disclosed by email. Subjects may decline to release their name and device serial numbers, however they will be informed that they will not have a warranty on their hearing aids in that case.

Information and/or Specimen Management

Electronic data will be kept in a database that resides behind the VA firewall. Hardcopy data and records (including ICFs, etc.) will be stored in a locked file cabinet in a locked office ([name]).

Data and Safety Monitoring Plan (DSMP)

1. *What safety information will be collected, including serious adverse events and unanticipated problems involving risk?* The safety information collected will include serious adverse events reported by participants, unanticipated problems involving risk, and leaving the study before the protocol is complete. Hearing will be evaluated at baseline, and again at the final visit to document any change in hearing. (A change in hearing due to study participation is not expected.)
2. *How the safety information will be collected, e.g., case report forms, at study visits, by telephone, etc.* The study data will be collected and recorded by a study audiologist, trainee, and/or research coordinator/assistant. The data will be entered into a research database stored on the VAPORHCS server. Serious events are not expected, and thus, if they occur, would likely be reported to the study team by the participant.
3. *The frequency of data collection, including when safety data collection starts.* Information will be collected at each study visit, and if anything comes up between visits.
4. *The frequency or periodicity of review of cumulative safety data (e.g., at a Data Safety Monitoring Board quarterly meeting, by the PI weekly, etc.).* Summary reports of study data will be generated for discussion at weekly meetings. Safety information will be reported to the PI as it is collected.
5. *Who will have oversight over the safety data?* Principal Investigator
6. *Describe the individual or group that will monitor the data and safety of the protocol and provide general description of the expertise of the person/membership and/or board/group as a whole.* Principal Investigator
7. *Which conditions would trigger an immediate suspension of the research? For example, efficacy proven, halted by DSMB due to unforeseen safety data, etc. (if applicable).* It is not expected that any event will occur that would trigger an immediate suspension of the research. If unexpected events do occur, the PI may decide, to halt the study due to unforeseen safety problems.

If any feedback is received from research participants indicating they may have experienced harm because of study participation, the incident will be immediately reported to the IRB. All electronic study data will be backed up on the VA secure server. Interview recordings and summaries will also be backed up on the server. Digital recorders and hard copy data (e.g., subject charts, and interview field notes) will be kept in a locked cabinet within a locked office. All analysis datasets will be deidentified. In the unlikely event of a breach of confidentiality, the incident will be reported to the IRB within the required timeframe and any resulting actions required and/or recommended by the IRB, Information Security and Privacy Offices will be taken promptly.

Step-by-Step Guidance on Conducting the Study

Hearing Aid Study

Recruitment

- Send recruitment letters to potential candidates identified via a CDW data pull.
- Post ads at the VAPORHCS (e.g., audiology, primary care, women's health clinics) and in the surrounding community
- Contact previous participants in NCRAR research studies

Telephone Screening

- Screen candidates over the phone using screening script, including administration of the Tinnitus and Hearing Survey (THS)
- If eligible, gather information from candidate and schedule initial appointment

Initial Appointment

- Administer informed consent
- Conduct conventional audiometric testing in sound-attenuated suite
- Exclude candidates if they reveal significant conductive hearing loss—as defined above. Tympanometry may be used to confirm middle ear function
- Ensure candidates have no active middle-ear disease and that hearing thresholds are within acceptable levels (25 dB HL or better at audiometric frequencies from .25-4 kHz)
- Candidates who fail to meet any of the inclusion criteria are considered screen fails and are not enrolled in the study. They are paid \$20 for attending the visit and do not complete the rest of the study visit procedures.
- Candidates who meet all inclusion criteria are enrolled in the study.
- Subjects complete the following questionnaires and assessments: Tinnitus Baseline Questionnaire, Tinnitus Functional Index (TFI), Hearing Handicap Inventory, QuickSIN testing
- All participants will receive hearing aids. Hearing aids will be programmed using the NAL-NL2 formula (Keidser, Dillon et al. 2012). Real-ear measures, in addition to participant feedback, will be used to verify and adjust the amplification settings. Hearing aids may be adjusted if necessary. Participants will be asked to use the hearing aids daily.
- Participants are paid \$20 for attending the appointment

2-3 Week Follow-up Visit

- Tinnitus counseling will be reviewed for all participants.
- The research audiologist will check the performance of the hearing aids, retrieve the data-logging information, and provide any necessary instructions to participants to

ensure they are using the devices properly. If needed, adjustments will be made to the gain settings of the hearing aids.

- Participants will fill out the TFI, HHI, and IOI-HA.
- Participants are paid \$20 for completing the visit.

3 Month Follow-Up Visit

- Participants will return 3 months after baseline to complete the study.
- A hearing evaluation of air conduction thresholds will be repeated to document any hearing change (or lack thereof).
- Subjects complete the following questionnaires and assessments: Tinnitus Functional Index (TFI), Hearing Handicap Inventory, IOI-HA, and QuickSIN testing
- Subjects then complete an exit interview regarding their experience with the hearing aids
- The research audiologist will again check the performance of the hearing aids, retrieve the data-logging information, and answer any questions. If needed, adjustments will be made to the gain settings of the hearing aids. Participants will be allowed to keep the hearing aids following this visit.
- Subjects are paid \$20 at this visit.

Schedule of Tests/Outcomes

Measure	Screen	Baseline	2-3 weeks	3 months
Tinnitus and Hearing Survey (THS)	X			
Inspect ear canal and ear drum		X	X	X
Tympanometry		X		X
Hearing test		X		X
Hearing aid assessment and fitting		X		
Real Ear testing		X		X
Speech in Noise test (QuickSIN)		X		X
Tinnitus Baseline Questionnaire		X		
Tinnitus Functional Index (TFI)		X	X	X
Hearing Handicap Inventory (HHI)		X	X	X
International Outcome Inventory for Hearing Aids (IOI-HA)			X	X
Tinnitus Counseling		X	X	
Exit Interview				X
Total Time	15 min	3 hrs	1.5 hrs	2 hrs

VA Clinician Interviews

Recruitment.

- Send survey via email to the VA Audiology email list to ask if they:
 - fit low-gain hearing aids on Veterans with bothersome tinnitus and normal hearing

- are willing to participate in a brief telephone interview

Telephone Interview Scheduling

- Interviewees will be selected from those email survey respondees who volunteer for interviews
- Those selected will be contacted by email or phone to schedule the telephone interview

Telephone Interviews

- The information sheet will be sent to the participant prior to the interview
- At the beginning of the interview phone call, the interviewer will confirm that the participant received the information sheet, and will read a spoken consent script. An audio-recording will be made of the participant giving spoken acknowledgement of consent to be interviewed and giving spoken consent to be audio-recorded during the interview. After an audio-recording of acknowledgment of consent has been made, then the interview questions (which will be audio-recorded) will begin.
- Interview questions will cover clinician attitudes on providing hearing aids for people with bothersome tinnitus and normal hearing.
- A notetaker will be present with the interviewer to take notes during the interview.

References & Literature Cited

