There is some limited, published, evidence that patients with normal hearing thresholds are willing to use mild amplification, and that is safe to do so. A study was conducted in which 19 subjects with normal hearing threshold were fit with hearing aids adjusted to provide mild amplification⁶. The amplification was being provided for the purposes of addressing reported hearing handicap. Seventeen subjects completed the trial period and their hearing thresholds were tested at the beginning and end of the trial with no change in thresholds. Of the original 19 subjects, one dropped out the study because he found the hearing aids to be too loud, and one was dropped from the study because he lost one of the hearing aids. Of the 17 who remained in the study, data logging indicated that they were wearing the hearing aids approximately 1-4 hours per day. Hobson et al⁹ concluded, based on their review of numerous studies, that hearing aids used for tinnitus management did not present any safety concerns.

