Documentation of informed consent will be acquired at the beginning of the first appointment. The candidate will sit in a room (usually sound booth or control room) with a member of the study team to review the information provided in the informed consent form. Once the candidate understands the content of the informed consent form, the candidate may sign the written consent form and a Health Insurance Portability and Accountability (HIPAA) acknowledgement form to indicate their agreement to participate in all study procedures. Testing will begin after informed consent has been documented. Additionally, as part of the informed consent process the subject will have the opportunity to agree to add their data to the Audiology and Rehabilitation Research Data Repository (MIRB #3750, P.I. [name].) for future research and recruitment.

VA Clinician Interviews

An information sheet describing the study along with its risks and benefits will accompany the email survey sent to approximately 200 VA audiologists, via the National Audiology listserv. The information sheet will inform the recipients of the email of the purpose of the study and what will be done with the information received. Anyone who does not consent, need not reply to the email. Clinicians interested in participating will be scheduled for a telephone appointment. At the beginning of the phone call, the interviewer will confirm that the participant received the information sheet and will read a spoken consent script. If the clinician wishes to participate, then an audio-recording will be made of the participant giving spoken acknowledgement of consent to be interviewed and giving spoken consent to be audio-recorded during the interview. After an audio-recording of acknowledgment of consent has been made, then the interview questions (which will be audio-recorded) will begin.

Risks and Side Effects:

Hearing Aid Study

It is possible that faulty equipment might present sounds at too high a level, although this has never happened in the research team's experience over many years of testing, and the equipment and software are typically designed so that such errors would be extraordinarily unlikely. Nonetheless, participants will be encouraged to alert the experimenter if any sound is uncomfortably loud and to feel free to remove or turn off the sound-producing devices at any time if they so wish.

VA Clinician Interviews

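### The plan has no prompted recording of non-serious events, so its tolerability data may come mainly from participants who complete the study

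*Combined protocol and SAP*

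**What the plan says.** The Data and Safety Monitoring Plan (DSMP) in the combined protocol and SAP covers the point in several places.

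- Item 1, content: "The safety information collected will include serious adverse events reported by participants, unanticipated problems involving risk", and departure before the protocol is complete. The same item adds: "Hearing will be evaluated at baseline, and again at the final visit to document any change in hearing".
- Item 2, method: it names the staff who record data and the database, then says "Serious events are not expected, and thus, if they occur, would likely be reported to the study team by the participant". It describes no form or question.
- Item 3, timing: "Information will be collected at each study visit, and if anything comes up between visits".
- Closing text: "If any feedback is received from research participants indicating they may have experienced harm because of study participation", the incident goes to the IRB. No seriousness threshold is attached.

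Outside the DSMP:

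- Risks and Side Effects says that "participants will be encouraged to alert the experimenter if any sound is uncomfortably loud".
- The Schedule of Tests/Outcomes places the TFI and an ear inspection at baseline, 2-3 weeks and 3 months. It places the exit interview at 3 months only and has no adverse-event row.
- Statistical Analysis for the hearing aid study fits a mixed model with a baseline mean and a mean at each follow-up, and reads benefit from the contrasts. It has the exit interview summarise comfort with the devices and with the amplification.
- Scientific Rationale and Significance describes an earlier mild-gain study in 19 normal-hearing people, of whom "one dropped out the study because he found the hearing aids to be too loud".

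**The concern.** The harms one would foresee from amplifying sound for people with normal thresholds and bothersome tinnitus are mostly not serious: sounds that are too loud, an irritated ear, tinnitus that feels worse. The protocol's own background supplies an example in the loudness dropout. Yet the listed safety content has no place for such events, and loudness is something participants are invited to raise rather than something staff ask about.

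This matters because the study is titled a feasibility and acceptability study, and its rationale says it will inform whether and how to run a randomised trial. Tolerability is part of acceptability. If discomfort is described mainly by those who reach Visit 3, the next trial would be designed on an account that omits the people who found the devices hardest to tolerate.

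**Working it through.** There is no plan figure to reproduce. The documents give no expected harm rate, no reporting rate and no sample-size derivation. The check is therefore a comparison of the DSMP with the visit steps, the schedule and the analysis section.

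**Step 1: what each route captures.**

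| Possible harm | At 2-3 weeks | At 3 months | Listed or counted as safety data |
|---|---|---|---|
| Change in hearing | Not tested | Air-conduction thresholds | Yes, DSMP item 1 |
| Worse tinnitus | TFI | TFI | No; analysed as mean change |
| Ear irritation or pain | Inspection (visible signs only) | Inspection; exit interview on comfort | No |
| Uncomfortable loudness | No question described; device check, and gain adjusted if needed | Exit interview on comfort with amplification | No |

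The seven dimensions described for the IOI-HA do not include loudness or ear discomfort, so that questionnaire does not fill the gap.

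**Step 2: what the TFI analysis can show.** A contrast of means does not identify individuals who deteriorate. As an illustration, take the 13 points that Outcome Measures gives as a meaningful reduction and apply it as a rise in one of 20 participants, all with data. The mean moves by 13/20 = 0.65 points. A change of that size in one person could easily sit inside an overall improvement. No section says that individual rises will be counted.

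**Step 3: what happens to an early leaver.**

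- The departure is recorded (DSMP item 1).
- No section requires the reason to be recorded.
- The exit interview is scheduled only at 3 months, and no contact at withdrawal is described.
- Someone who leaves before Visit 2 would have no follow-up TFI or ear inspection. Someone who leaves after Visit 2 would have those but no comfort interview.

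**Step 4: how many people this might touch.** The only related figure is the loudness dropout in the cited study: 1/19 = 5.3%, exact 95% interval 0.1% to 26.0%. Carried to about 20 participants, that is 20 × 1/19 = 1.05 such leavers, with a range of 20 × 0.001 = 0.02 to 20 × 0.260 = 5.2. This is an illustration from one small study. It shows that the case is foreseeable; it does not measure a bias.

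**The case against.** The strongest reply is that the plan collects more than the first sentence of DSMP item 1 suggests. Hearing is tested at both ends of the study. Information is gathered at each visit and in between, harm feedback of any seriousness goes to the IRB, and summaries of study data are discussed weekly. Participant feedback is used in setting the aids, and loud sounds are not to be amplified. In a single-group pilot of about 20 people using commercially available devices, what is left is a refinement of recording and reporting. The exit interview and other instruments are listed only by title in the appendix, so their items cannot be checked, and the words about participant reporting do not themselves say unprompted.

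Most of this stands, and it rules out several stronger readings that a reader might infer:

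- *That safety collection is confined to serious events, unanticipated problems and withdrawals.* It is not; the hearing evaluation is in the same item.
- *That none of the likely harms is asked about.* Wrong for tinnitus impact, which the TFI measures at both follow-ups, and too strong for comfort, which the exit interview covers.
- *That events will be under-counted by a calculable amount.* One could multiply 1/19 by an assumed share of events volunteered and derive a lower chance of seeing any case. But that event was a dropout, which item 1 records whether or not a complaint is voiced, and the documents give no volunteering rate.
- *That the limit for zero events shows the defect.* The two-sided 95% upper limit for 0 of 20, 1 − 0.025^(1/20) = 16.8%, depends only on the sample size and is the same however events are sought.
- *That recognition of worsening is delayed, or that a formal safety conclusion is planned.* There is a TFI at 2-3 weeks and weekly review, and no such conclusion is stated.

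What the reply does not answer is narrower. Item 3 sets when information is gathered, not what is asked. The IRB route operates only if feedback arrives. Ear inspection sees visible signs, not pain or loudness. None of these reaches the early leaver.

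**Conclusion.** The point holds in a limited form. The plan describes no prompted recording of non-serious events, does not say that TFI worsening or ear findings will be tabulated as safety data, and obtains its account of comfort only at Visit 3. Tolerability and acceptability may therefore be biased toward completers. The direction is plausible; the size cannot be derived from the documents.

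This rests on two assumptions: that the visit steps and schedule are a complete account of what is asked before Visit 3, and that some participants will leave early for reasons of comfort. If the unseen forms already contain such questions, only the early-leaver gap and the missing tabulation remain. It does not undermine the TFI analysis. It should be corrected because the remedy is cheap and acceptability is a main product of the study.

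**What to change.** 1. Add to DSMP items 1 and 2, to both follow-up visits in the Step-by-Step Guidance, and as a row in the Schedule of Tests/Outcomes, a short fixed question set at Visits 2 and 3: sounds uncomfortably loud, ear pain or irritation, tinnitus worse, other. Record date, severity and outcome.
2. Put the same questions by telephone, with the reason for stopping, to anyone who leaves early and is willing to answer. Keep the call voluntary, since participants may withdraw freely.
3. In Statistical Analysis, state that counts will be reported among all fitted participants, together with ear-inspection findings and the number whose TFI rose by a prespecified amount. Show how many have no follow-up TFI. If 13 points is used, say that Outcome Measures supports 13 only as a meaningful reduction and that its use for worsening is an assumption.

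The cost is one short form, a few minutes per visit, a brief call to early leavers and one table. The downside is that solicited counts will be higher than spontaneous ones, so the report should say that the events were prompted.

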Assessment Visit (Visit 1). After qualifying over the telephone, individuals will be scheduled for an appointment (Visit 1) at the NCRAR to undergo an assessment to determine study candidacy. Following informed consent, participants will complete standard audiologic testing (air and bone conduction hearing thresholds, speech audiometry, immittance audiometry, and hearing aid assessment). During the audiologic exam, any physical issues that would interfere with the participant wearing hearing aids will be identified, and may result in exclusion from participation. If participants meet all criteria, and they are willing to participate, they will be enrolled in the study. Once enrolled, participants will complete the Tinnitus Functional Index (TFI)²⁰, the Hearing Handicap Inventory (HHI), and Tinnitus Questionnaire Baseline.

Enrolled participants (N=20) will be fit with commercially available receiver-in-canal (RIC) hearing aids with optional sound generator and streaming at the first study visit. Participants will be fit using manufacturer-provided ear-domes. Using the NAL-NL2 formula²², real-ear measures, in addition to patient feedback, will be used to verify and adjust the amplification settings. The hearing aids will be adjusted to be acoustically transparent for loud sounds (no loud sounds will be amplified), while providing mild amplification based on NAL-NL2 targets for soft and moderate inputs. The instruments will have data-logging capability, i.e., the number of hours the devices are used per day will be logged for later retrieval by the audiologist. Tinnitus counseling will occur immediately following the fitting and adjustment of the instruments.

All participants will receive scripted tinnitus counseling, which was used in our two previous hearing aid studies^{10, 11}. The counseling, which describes how sound can be used to improve comfort with tinnitus, will follow pp. 31-64 in the flip-chart counseling book *Progressive Tinnitus Management: Counseling Guide*²³, and will require about 15 minutes.

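### At the 2-3 week visit the TFI and HHI are listed after the counseling review and device work, unlike at the other two visits, and nothing in the plan requires the questionnaires to come first

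*Combined protocol and SAP*

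**What the plan says.** The protocol's closing operational section is headed "Step-by-Step Guidance on Conducting the Study". Its list for the 2-3 week follow-up visit has this order:

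1. "Tinnitus counseling will be reviewed for all participants".
2. The audiologist checks the aids, retrieves the usage log and gives instructions. "If needed, adjustments will be made to the gain settings of the hearing aids".
3. "Participants will fill out the TFI, HHI, and IOI-HA".
4. Payment.

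The initial appointment list puts the TFI and HHI before the bullet in which hearing aids are received. The Assessment Visit (Visit 1) narrative agrees: questionnaires on enrollment, then the fitting, and "Tinnitus counseling will occur immediately following the fitting and adjustment of the instruments".

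The 3-month list puts the questionnaires after the hearing test. Next comes "Subjects then complete an exit interview regarding their experience with the hearing aids", and after that "The research audiologist will again check the performance of the hearing aids". No counseling is scheduled at that visit.

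The Follow-up Visit (Visit 2) narrative does not mention questionnaires. The Schedule of Tests/Outcomes shows which measures fall at which visit, not their order within it.

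**The concern.** The TFI is the primary outcome and the HHI is a secondary one. Both are self-reported, by people who know they are wearing the devices, in a single group of 20 with no comparison arm to absorb an effect of staff contact. The counseling teaches participants to use sound to be more at ease with their tinnitus, which is close to what the TFI asks about. A score taken just after that talk, and after a device problem may have been fixed, could partly reflect the appointment and not only the preceding weeks of use.

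The Statistical Analysis section for the hearing aid study estimates a mean at each follow-up and reads each contrast with baseline as the benefit of treatment. The 2-3 week contrast is one of only two such contrasts for the TFI. The pilot is also meant to inform whether and how to run a randomized trial, so the early and late scores should be collected under like conditions.

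**Working it through.** The plan gives no figure to reproduce here: no SD, power, effect size or estimate of a contact effect. The check compares the listed orders and then traces the consequence through the planned model.

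**Listed order by visit (step-by-step guidance, with the visit narratives)**

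| Visit | Listed before TFI/HHI | Listed after TFI/HHI | Does the narrative settle the order? |
|---|---|---|---|
| 1 (baseline) | Consent, audiometry, eligibility | Fitting and adjustment | Yes: TFI and HHI, then fitting, then counseling |
| 2 (2-3 weeks) | Counseling review, device check, instructions, any gain change | Payment | No: questionnaires not mentioned |
| 3 (3 months) | Air conduction thresholds | Exit interview, device check, any gain change | Supports the list: outcome measures and interview described before the final device check |

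The feature particular to Visit 2 is therefore narrow. Same-day contact of some kind precedes the questionnaires at every visit, because audiometry comes first at Visits 1 and 3. Only counseling and device work precede them at Visit 2 alone, and the gain change is conditional.

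**How far the bullets can be read as a sequence.** The Outcome Measures section requires aided QuickSIN at Visit 1, yet the Visit 1 list names QuickSIN before the aids are received. That list also leaves out the Visit 1 counseling. So the bullets are not strictly chronological. For Visit 2, however, no other text supplies a different order.

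**Effect on the planned contrasts.** Let m0, m2 and m3 be the mean scores at baseline, 2-3 weeks and 3 months if questionnaires are completed before any counseling or device work. Let b be the average shift in the Visit 2 score from same-day counseling and adjustment, if the listed order is followed.

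- Visit 2 minus baseline: (m2 + b) − m0 = (m2 − m0) + b. Shifted by b.
- Visit 3 minus baseline: m3 − m0. Not shifted, because the model has a separate mean at each time point and the Visit 2 mean absorbs b.
- Visit 3 minus Visit 2, if anyone computes it: (m3 − m2) − b. The Statistical Analysis section does not plan this contrast.

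**Which outcomes are reached.** The modeled outcomes are the TFI, the hearing handicap inventory (named there as the HHIA) and QuickSIN. QuickSIN is not done at Visit 2. The IOI-HA has no baseline and is not modeled. That leaves the 2-3 week TFI and HHI contrasts.

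**Size of b.** It cannot be derived. The questionnaire forms are listed in the Appendix but not shown, so the recall period, which would limit how far a same-day event can move the score, is not available. The only scale in the documents is the TFI reduction of about 13 points described as meaningful for an individual patient. That is not a yardstick for a shift in a group mean.

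**The case against.** The strongest reply is that bullet order is not a protocol requirement. The Visit 1 list is demonstrably out of sequence for aided QuickSIN. The recruitment bullets in the same section are parallel or fallback routes, not steps. Where the authors mean a sequence they use words such as then or immediately, and the Visit 2 questionnaire bullet has no such word. The first two Visit 2 bullets closely repeat the Visit 2 narrative, so the questionnaire line may simply have been added beneath reused text. All of this stands, and it means the plan leaves the order open more than it prescribes a bad one. It does not remove the need for a fix: staff have no other guidance for that visit, and an open order may vary between participants.

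A second reply is that little rests on the 2-3 week score. The study is a pilot without a hypothesis, no decision rule uses that score, and everyone has already been counseled at Visit 1, so the Visit 2 score carries counseling under any order. This also stands. What is added is only a same-day repeat plus any adjustment, which limits the point to a minor one.

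A reader might infer more: that the 2-3 week scores are contaminated, that only Visit 2 scores follow same-day staff contact, or that the main 3-month result is biased. The documents support none of these. The order is listed but not mandated, audiometry precedes the questionnaires at Visits 1 and 3, and the 3-month contrast does not contain b.

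**Conclusion.** The point holds in a limited form, and its severity is minor. The Visit 2 TFI and HHI are listed after counseling review and device work, the other two visits list them before fitting or device work, and no text requires questionnaires first. If the listed order is followed, the 2-3 week contrasts with baseline for the TFI and HHI are shifted by an amount b of unknown size and direction.

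This rests on two conditions: that staff treat the list as the running order, and that same-day counseling or adjustment moves the answers at all. The documents establish neither. Expressing b in points or as a share of the 13-point threshold would only restate an assumption, so no magnitude is claimed. The point is still worth acting on because the remedy is almost free and an order effect in the collected scores cannot be separated out afterwards.

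**What to change.** In the Follow-up Visit (Visit 2) and Final Visit (Visit 3) narratives, and in the step-by-step guidance, state that at each follow-up visit the TFI and HHI, and the IOI-HA where it is given, are completed before the counseling review, device check or any gain adjustment. Move the questionnaire bullet to the top of the 2-3 week list.

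The words where it is given matter. The Outcome Measures section places the IOI-HA at Visit 3 only, while the step-by-step guidance and the Schedule of Tests/Outcomes also place it at 2-3 weeks. Those places should be reconciled in the same edit.

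The cost is a sentence and one moved bullet, with no added visit time, procedure or participant burden. If some participants have already been seen, record for each whether the Visit 2 questionnaires came before or after counseling and device work, and report this alongside the 2-3 week contrast.
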